6.7 Home visits

During the 52-week Treatment Period, the at-home visits will be conducted by fully trained healthcare professional visiting the study participant at his or her home. Alternatively, these visits can be conducted at the site as deemed necessary by site personnel and/or the study participant. For home/self-dosing, the same safety monitoring schedule will be followed as per onsite dosing. The home nurse will be present during the full duration of the visit. Home visits can be conducted if the following conditions are met:

- The study participant is willing to be dosed and monitored at home by a home nurse.
- The study participant has shown good acute tolerability to previous administrations of IMP (namely, he or she must have had no moderate or severe infusion reactions or other AEs that the Investigator considers could increase the risk of home administration).

The Investigator should complete a checklist to confirm that criteria for home self-administration have been fully evaluated.

6.8 Treatment after the end of the study

Study participants who complete participation in MG0004 may have the possibility to continue receiving rozanolixizumab through a managed access program as per applicable local regulations.

In the case of prolonged hypogammaglobulinemia after treatment discontinuation, study participants can be considered for treatment with prophylactic antimicrobial therapy per local

guidelines. Study participants must be followed up until IgG levels return to values within the normal range or to individual Baseline values.

7 DISCONTINUATION OF STUDY MEDICATION AND PARTICIPANT DISCONTINUATION/WITHDRAWAL

[figure not shown]
7.1 Discontinuation of study medication

7.1.1 Liver chemistry stopping criteria

Discontinuation of study treatment for abnormal liver function should be considered by the Investigator when a participant meets one of the conditions outlined [Figure 7-1](#) or if the Investigator believes that it is in best interest of the participant.

The study participant should follow the visit schedule as described in the protocol and complete the eCRF accordingly.

Figure 7-1: Liver chemistry stopping criteria and increased monitoring algorithm

[figure not shown]

ALT=alanine aminotransferase; AST=aspartate aminotransferase; INR=international normalized ratio; SAE=serious adverse event; ULN=upper limit of normal

* The INR value is not applicable to study participants on anticoagulants.

Treatment with study medication may be continued with increased monitoring if a study participant meets one of the criteria outlined in [Figure 7-2](#).

Figure 7-2: Liver chemistry increased monitoring algorithm with continued study intervention for participants with ALT at least 3xULN but less than 8xULN

ALT=alanine aminotransferase; AST=aspartate aminotransferase; bili=bilirubin; INR=international normalized ratio; SAE=serious adverse event; ULN=upper limit of normal

Specific assessments and follow-up actions for potential drug induced liver injury (PDILI) are provided in Appendix 6 (Section 10.6).

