7.1.3 Discontinuation of study medication due to other AEs or medical conditions

A study participant **must** permanently discontinue study medication if any of the following events occur:

1. Study participant develops an illness that would interfere with his or her continued participation.
2. Study participant has new onset or recurrent neoplastic disease (except for superficial basal or squamous cell carcinoma of the skin not requiring targeted biological therapy, chemotherapy or radiation)
3. Study participant has a serious infective episode requiring hospitalization or IV antibiotic therapy (including but not limited to bacteremia or sepsis, meningitis, osteomyelitis or septic arthritis, pneumonia, or visceral abscess).
4. Study participant meets potential drug-induced liver injury (PDILI) permanent discontinuation criteria.
5. Study participant has a TB test that is confirmed positive or any further evidence suggestive of potential TB infection (ie, exposure) and further examinations result in a diagnosis of active TB or latent TB infection (LTBI).
6. If a nontuberculosis mycobacterium infection (NTMB) is identified during a study, the same withdrawal procedures as those used for an active TB infection identified during the study should be followed.
7. Study participant experiences a serious AE of headache which is considered related to the study medication in the opinion of the Investigator.
8. Study participant has an AE of severe or serious infusion or anaphylactic reaction requiring corticosteroid and/or epinephrine therapy (see Section 10.22) (Sampson et al, 2006).

Study participants **may** permanently discontinue study medication at the discretion of the Investigator, Medical Monitor, and Study Physician if any of the following events occur:

9. Study participant is noncompliant with the study procedures or medications in the opinion of the Investigator.
10. Study participant takes prohibited concomitant medications as defined in this protocol.

Investigators should contact the Medical Monitor, whenever possible, to discuss the withdrawal of a participant in advance. Investigators should attempt to obtain information on study participants in the event of withdrawal (eg, reason for withdrawal, any safety information).

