10.6 Appendix 6: Liver Safety – Suggested Actions and Follow-up Assessments

Participants with PDILI must be assessed to determine if study medication must be discontinued. In addition, all concomitant medications and herbal supplements that are not medically necessary should also be discontinued.

Investigators should attempt to obtain information on study participants in the case of study medication discontinuation to complete the final evaluation.

Study participants with PDILI should not be withdrawn from the study until investigation and monitoring are complete. All results of these evaluations and observations, as well as the reason(s) for study medication discontinuation and/or participant withdrawal (if applicable), must be recorded in the source documents. The eCRF must document the primary reason for discontinuation of study medication.

A specific monitoring plan must be agreed between the UCB study physician and the Investigator for study participants who have ALT >5xULN. The monitoring plan should include any necessary follow-up assessments (until resolution of the abnormal lab values).

Phase 3 liver chemistry stopping criteria are designed to assure participant safety and to evaluate liver event etiology. Stopping criteria are presented in [Table 10-2](#) and increased monitoring criteria are presented in [Table 10-3](#).

Table 10-2: Phase 3 liver chemistry stopping criteria and follow-up assessments

Liver Chemistry Stopping Criteria	
ALT-absolute	ALT ≥8xULN
ALT increase	ALT ≥5xULN but <8xULN persists for ≥2 weeks ALT ≥3xULN but <5xULN persists for ≥4 weeks
Bilirubin^{a, b}	ALT ≥3xULN and bilirubin ≥2xULN (>35% direct bilirubin)
INR^b	ALT ≥3xULN and INR >1.5, if INR measured
Cannot mMonitor	ALT ≥5xULN but <8xULN and cannot be monitored weekly for ≥2 weeks ALT ≥3xULN but <5xULN and cannot be monitored weekly for ≥4 weeks
Symptomatic^c	ALT ≥3xULN associated with symptoms (new or worsening) believed to be related to liver injury or hypersensitivity
Suggested Actions and Follow-up Assessments	
Actions	Follow-up Assessments

This document cannot be used to support any marketing authorization application and any extensions or variations thereof.

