
• Immediately discontinue study medication.• Report the event to the Sponsor within 24 hours.• Complete the liver event eCRF, and complete as SAE data collection tool if the event also met the criteria for an SAE. ^b• Perform liver chemistry follow-up assessments.• Monitor the participant until liver chemistry test abnormalities resolve, stabilize, or return to baseline (see MONITORING).• Do not restart/rechallenge participant with study medication.• If restart/rechallenge not allowed per protocol or not granted, permanently discontinue study medication and continue participant in the study for any protocol specified follow-up assessments. Consider the need for a toxicology screening. 
MONITORING:
 
For bilirubin or INR criteria
 
• Repeat liver chemistry tests (include ALT, AST, alkaline phosphatase, bilirubin) and perform liver event follow-up assessments within 24 hours.• Monitor participant twice weekly until liver chemistry test abnormalities resolve, stabilize, or return to Baseline.• A specialist or hepatology consultation is recommended. 
For all other criteria
 
• Repeat liver chemistry tests (include ALT, AST, alkaline phosphatase, bilirubin) and perform liver chemistry follow-up assessments within 24 to 72 hours.• Monitor participants weekly until liver chemistry abnormalities resolve, stabilize, or return to Baseline.	
• Viral hepatitis serology. ^d• Obtain INR and recheck with each liver chemistry assessment until the transaminases values show downward trend.• Only in those with underlying chronic hepatitis B at study entry (identified by positive HBsAg), quantitative hepatitis B DNA and hepatitis delta antibody. ^e• Obtain blood sample for PK analysis as soon as feasible after the most recent dose. ^f• Serum CPK and LDH.• Fractionate bilirubin, if total bilirubin $\geq 2xULN$.• Obtain complete blood count with differential to assess eosinophilia.• Record the appearance or worsening of clinical symptoms of liver injury, or hypersensitivity, on the AE report form.• Record use of concomitant medications (including acetaminophen, herbal remedies, and other over-the-counter medications) on the concomitant medications eCRF.• Record alcohol use on the liver event alcohol intake eCRF.• Exclude pregnancy.• Urine drug screen. 
For bilirubin or INR criteria:
 
• Anti-nuclear antibody, anti-smooth muscle antibody, Type 1 anti-liver kidney microsomal antibodies, and quantitative total IgG or gamma globulins.• A serum acetaminophen adduct assay for assessing the potential acetaminophen contribution to liver injury in participants with definite or likely acetaminophen use in the preceding week.

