- ^f Record the date/time of the PK blood sample draw and the date/time of the last dose of study medication prior to the PK blood sample draw on the eCRF. If the date or time of the last dose is unclear, provide the participant’s best approximation. If the date/time of the last dose cannot be approximated OR a PK sample cannot be collected in the time period indicated above, do not obtain a PK sample. Instructions for sample handling and shipping are in the IMP Handling Manual.

Table 10-3: Phase 3 liver chemistry increased monitoring criteria with continued study medication

Liver Chemistry Increased Monitoring Criteria	
Criteria	Actions

ALT $\geq 5xULN$ and $< 8xULN$ and bilirubin $< 2xULN$ without symptoms believed to be related to liver injury or hypersensitivity, and who can be monitored weekly for 2 weeks.
 
OR
 
ALT $\geq 3xULN$ and $< 5xULN$ and bilirubin $< 2xULN$ without symptoms believed to be related to liver injury or hypersensitivity, and who can be monitored weekly for 4 weeks.
	
 • Notify the Sponsor Medical Monitor within 24 hours of learning of the abnormality to discuss participant safety. • Participant can continue study medication. • Participant must return weekly for repeat liver chemistry tests (ALT, AST, alkaline phosphatase, bilirubin) until the abnormalities resolve, stabilize, or return to baseline. • If at any time, the participant meets liver chemistry stopping criteria, proceed as described in Section 7.1.1. • If ALT decreases from ALT $\geq 5xULN$ and $< 8xULN$ to $\geq 3xULN$ but $< 5xULN$, continue to monitor liver chemistries weekly. • If, after 4 weeks of monitoring, ALT $< 3xULN$ and bilirubin $< 2xULN$, monitor participants twice monthly until liver chemistry tests resolve, stabilize, or return to baseline.

ALT=alanine aminotransferase; AST=aspartate aminotransferase; ULN=upper limit of normal

10.7 Appendix 7: Medical device incidents – definition and procedures for recording, evaluating, follow-up, and reporting

Not applicable.

PUBLIC COPY
This document cannot be used to support any marketing authorization application and any extensions or variations thereof.

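### Protocol Sections 7.1.1 and 7.1.3 and Appendix 6 give liver stopping different status, so continued dosing can comply with one and breach another

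*Protocol*

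**What the plan says.** Protocol Section 7.1.1, on liver chemistry stopping criteria, states: "Discontinuation of study treatment for abnormal liver function should be considered by the Investigator when a participant meets one of the conditions outlined" in Figure 7-1, or when the investigator thinks stopping is in the participant's best interest. It refers to Appendix 6 for the assessments and follow-up of potential drug-induced liver injury (PDILI).

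Protocol Section 7.1.3 opens its binding list with "A study participant must permanently discontinue study medication if any of the following events occur". Item 4 of that list is "Study participant meets potential drug-induced liver injury (PDILI) permanent discontinuation criteria". The section also has a separate list of events for which stopping is left to judgement. Liver injury is not on that second list.

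Protocol Appendix 6 begins with "Participants with PDILI must be assessed to determine if study medication must be discontinued". Table 10-2 then sets out the liver stopping criteria and, under the heading "Suggested Actions and Follow-up Assessments", lists among its actions "Immediately discontinue study medication" and "Do not restart/rechallenge participant with study medication". Table 10-3, on increased monitoring, adds: "If at any time, the participant meets liver chemistry stopping criteria, proceed as described in Section 7.1.1".

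Two further places bear on the point. Footnote a to the laboratory table in Appendix 2 describes the actions in Section 7.1.1 and Appendix 6 as required. Section 6.6 says that participants who meet the discontinuation criteria should be taken off rozanolixizumab.

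**The concern.** The status of the rule changes from place to place: something to consider, an obligation, an immediate instruction, a suggestion. These are different decisions for the same participant. Section 2.3 relies on the withdrawal and stopping criteria to contain risk, and Section 8 allows no waivers. Site staff and monitors therefore need to know whether continued dosing after a criterion is met is within the protocol or a deviation, and the text does not tell them.

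There is a smaller consequence for the analysis. Occurrence of TEAEs leading to permanent withdrawal of study medication is one of the two primary safety endpoints (Protocol Section 3, SAP Section 2.2.1.1). If investigators resolve the ambiguity differently, the same liver event can end in permanent withdrawal at one site and not at another. The study is open-label, so that judgement is made with the dose known.

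**Working it through.** The plan has no figure to reproduce here. The check sets the provisions side by side and then works one illustration.

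| Place in protocol | Trigger named | Status of stopping |
|---|---|---|
| Section 7.1.1 | A condition in Figure 7-1 (not shown) | To be considered by the investigator |
| Section 7.1.3, item 4 | PDILI permanent discontinuation criteria (undefined) | Obligatory and permanent |
| Appendix 6, lead text | PDILI | Assessment obligatory; stopping depends on it |
| Table 10-2 | The listed ALT, bilirubin, INR and symptom criteria | Immediate, no restart, but headed as suggested |
| Table 10-3 | Table 10-2 criteria met during monitoring | Refers back to Section 7.1.1 |
| Appendix 2, footnote a | Liver stopping or monitoring event | Actions described as required |
| Section 6.6 | Discontinuation criteria of Section 7.1 | Should be stopped |

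1. **Do the triggers coincide?** Section 7.1.1 and Table 10-2 carry the same name for their criteria, but the content of Figure 7-1 is not available. Section 7.1.3 item 4 cites neither. Table 10-2 is the only readable set of liver stopping criteria, so reading item 4 as pointing to it is natural. It remains an inference.

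2. **Can one course of action satisfy one provision and fail another?** Take a participant who meets a Table 10-2 criterion. The investigator considers stopping, documents the reasoning and continues dosing. The lead-in of Section 7.1.1 is met. The Table 10-2 instruction is not followed. On the natural reading of item 4, Section 7.1.3 is breached.

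3. **Do the cross-references settle it?** No. Section 7.1.1 points to Appendix 6, Table 10-3 in Appendix 6 points back to Section 7.1.1, and Appendix 2 points to both. None says which prevails.

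4. **Could the softer wording be a slip?** The neighbouring Section 7.1.2 on QTc says that a participant who meets a criterion will be withdrawn from study medication. Beside it, the liver wording can be read as a deliberate choice.

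5. **Who changes the endpoint count?** A participant must meet a stopping criterion, be kept on treatment where another section would stop treatment, and have the event recorded as a TEAE. Under Appendix 3 (Section 10.3.1) an abnormal laboratory result is an AE only if judged clinically significant, so not every criterion met qualifies.

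6. **Size per case (illustration).** SAP Section 3.9 gives a maximum of 240 participants. With 1:1 allocation that is 240/2 = 120 per dose. One discordant case moves a dose group's percentage by 1/120 = 0.8 points. With an assumed 50 treated per dose, the shift is 1/50 = 2.0 points. In the all-participants column at the maximum it is 1/240 = 0.4 points. SAP Section 8.2.2 groups TEAEs by the most recent dose, so actual dose-group denominators may differ from 120.

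**The case against.** The strongest reply has four parts.

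- **The missing figure.** Section 7.1.1 defers to an algorithm that is not visible and may contain its own stop instruction. Calling the section discretionary rests on its lead-in sentence. This stands as a limit on the finding. It does not remove the difference between that sentence and the readable text of Section 7.1.3 and Table 10-2.

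- **One course fits everything.** A site that stops treatment complies with every provision, and explicit permission to continue is tied to the monitoring criteria of Figure 7-2 and Table 10-3. As a matter of logic this is right, and it narrows the conflict to participants whom an investigator keeps on treatment. It does not close it: an instruction to consider an action is met by considering it, and Table 10-3 returns the reader to that instruction.

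- **Table 10-2 is not mandatory in itself.** A reader might infer that it is. Its heading calls the actions suggested, and the obligation comes from Section 7.1.3, through an undefined label. The objection stands, and the mix of imperative wording under that heading is part of what needs reconciling.

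- **Restart is not open.** A reader might infer from the bullet on restart not being allowed or granted that rechallenge is sometimes possible. The instruction before it already rules out restart, and that bullet also ends in permanent discontinuation. The documents do not support treating restart after a liver stop as a separate unresolved question.

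**Conclusion.** The protocol contradicts itself on the status of liver stopping, and this should be corrected mainly for patient safety. The finding rests on the readable text and on linking item 4 of Section 7.1.3 to Table 10-2, which is a reasonable inference but is nowhere stated.

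A reader might go further and conclude that every participant who meets a Table 10-2 criterion is or is not a primary-endpoint event according to the section the site follows. The documents do not support that. An investigator who considers stopping and stops produces the same record under every section, and some laboratory findings never become TEAEs. The effect is confined to the group in step 5 of the working. It falls on a descriptive percentage, because no hypothesis testing is planned (Protocol Section 9.7.1, SAP Section 4.1). The documents give no expected rate of liver stopping events, so only the effect per case can be stated, not the total.

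**What to change.** Reconcile Protocol Sections 6.6, 7.1.1 and 7.1.3, footnote a of Appendix 2, and the lead text, Table 10-2 and Table 10-3 of Appendix 6, so that one rule with one status appears throughout. In Section 7.1.3 item 4, name the table or figure that holds the PDILI permanent discontinuation criteria. Confirm at the same time that Figure 7-1 carries the same conditions and the same instruction. The choice of rule belongs to the sponsor and its clinical and safety advisers; this review does not say which is right.

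The cost is wording at the next protocol amendment and a clarification letter to sites. No change to the endpoint definition or the planned summaries is needed. As an optional extra, the liver listing already planned in SAP Section 8.3.1 could also show the action taken with study medication, so that any participant kept on treatment after meeting a criterion can be seen.

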7.1.2 QTc stopping criteria

If a clinically significant finding is identified after enrollment (including, but not limited to changes from Baseline in QT interval corrected using QT interval corrected for heart rate using Fridericia's formula [QTcF]), the Investigator or qualified designee will determine if the participant can continue in the study and if any change in participant management is needed. This review of the ECG printed at the time of collection must be documented. Any new clinically relevant finding should be reported as an AE.

A study participant who meets either bulleted criterion based on the average of triplicate ECG readings will be withdrawn from study medication and move into the Observation Period. The study participant should be referred to a specialist (ie, cardiologist) and managed as per local guidance.

- QTc >500 msec OR uncorrected QT >600msec
- Change from baseline of QTc >60msec

For participants with underlying bundle branch block, follow the discontinuation criteria listed below:

Baseline QTc with Bundle Branch Block	Discontinuation QTc Threshold with Bundle Branch Block
<450msec	>500msec
450 to 480msec	≥530msec

See the Schedule of Activities (Section 1.3) for data to be collected at the time of treatment discontinuation and follow-up and for any further evaluations that need to be completed.

The study participant should follow the visit schedule as described in the protocol and complete the eCRF accordingly.

7.1.3 Discontinuation of study medication due to other AEs or medical conditions

A study participant **must** permanently discontinue study medication if any of the following events occur:

1. Study participant develops an illness that would interfere with his or her continued participation.
2. Study participant has new onset or recurrent neoplastic disease (except for superficial basal or squamous cell carcinoma of the skin not requiring targeted biological therapy, chemotherapy or radiation)
3. Study participant has a serious infective episode requiring hospitalization or IV antibiotic therapy (including but not limited to bacteremia or sepsis, meningitis, osteomyelitis or septic arthritis, pneumonia, or visceral abscess).
4. Study participant meets potential drug-induced liver injury (PDILI) permanent discontinuation criteria.
5. Study participant has a TB test that is confirmed positive or any further evidence suggestive of potential TB infection (ie, exposure) and further examinations result in a diagnosis of active TB or latent TB infection (LTBI).
6. If a nontuberculosis mycobacterium infection (NTMB) is identified during a study, the same withdrawal procedures as those used for an active TB infection identified during the study should be followed.
7. Study participant experiences a serious AE of headache which is considered related to the study medication in the opinion of the Investigator.
8. Study participant has an AE of severe or serious infusion or anaphylactic reaction requiring corticosteroid and/or epinephrine therapy (see Section 10.22) (Sampson et al, 2006).

Study participants **may** permanently discontinue study medication at the discretion of the Investigator, Medical Monitor, and Study Physician if any of the following events occur:

9. Study participant is noncompliant with the study procedures or medications in the opinion of the Investigator.
10. Study participant takes prohibited concomitant medications as defined in this protocol.

Investigators should contact the Medical Monitor, whenever possible, to discuss the withdrawal of a participant in advance. Investigators should attempt to obtain information on study participants in the event of withdrawal (eg, reason for withdrawal, any safety information).

